4.6. INFORMED CONSENT

Informed consent will be taken from patients in a neurosurgical clinic after the diagnosis of a symptomatic pineal cyst is made, patient expresses interest in taking part in the study and passes through the inclusion and exclusion criteria as eligible for participation in the study.

A member of the research team will take informed consent. The person taking informed consent will be experienced in assessing capacity and aware of the ethical issues involved.

Participants will be provided with the current version of the REC-approved Patient Information Sheet for review.

Participants will be given the opportunity to ask any questions and only once all of their queries have been answered will the consent be taken by the Principal Investigator or suitably qualified, delegated member of the clinical care team. Patients will be informed that they can withdraw their consent at any time without giving reasons for doing so.

28/06/2021 Version 1.2

Date and Version No:

The process of obtaining a consent from patients who underwent an operation prior to the commencement of the study (see Amendment 1) is described in section 4.5.1. The Consent Form itself will be identical to those used for patients recruited after the date of commencement of the study. A tailored Patient Information Sheet will provide these patients with relevant information about study participation.

4.7. STUDY ASSESSMENTS

Assessment methods:

4.7.1. Questionnaires. - see above

4.8. DEFINITION OF END OF STUDY

The study will begin with at a given start date and will conclude after the last patient completes three-year questionnaire. (see also Flow Chart and Flow Table in the Appendix 7 and 8, respectively):

5. INTERVENTIONS

The only interventions in this study are questionnaires that the patients will be asked to fill in. Please see section 4.6.

As a result of Amendment 1, the patients who had undergone surgery prior to the commencement of the study have already filled in some or all required questionnaires for the purpose of clinical management and will only be asked for a permission to use them for the purpose of this research study. In addition, they will be prospectively asked to fill in questionnaires that are due at the predefined future time points.

6. SAFETY REPORTING

6.1 Safety data collection

This is an observational study where the only interventions are questionnaires and collection of clinical data. Nevertheless, this study presents an opportunity to systematically monitor surgical complications whose governance will fall into the realm of clinical rather than research governance. As such, we don't anticipate research-related events. Nevertheless, we will have system in place whereby any relevant events will feed into existing departmental governance structure.

7. STUDY COMMITTEES

Study Management Group

The Chief Investigator (CI) together with the research team are responsible for the day-to-day running of the study as detailed in study-specific procedures. They will work together as the Study Management Group and will meet monthly.

Study Steering Committee

It will consist of one independent neurosurgeon as the chair, one patient representative and one member of Study Management Group. The Study Steering Committee will monitor the conduct and progress of the study, including recruitment, data completeness and deviations from the protocol. The Study Steering Committee will meet every 6 months while participants are on treatment.

1. ETHICAL & REGULATORY CONSIDERATIONS

Consent

The Informed Consent form must be approved by the REC and must be in compliance with GCP, local regulatory requirements and legal requirements. The investigator must ensure that each study participant is fully informed about the nature and objectives of the study and possible risks associated with their participation.

The investigator will obtain written informed consent from each patient before any study-specific activity is performed. The informed consent form used for this study and any change made during the course of this study, must be prospectively approved by the REC. The investigator will retain the original of each patient's signed informed consent form.

Should a patient require a verbal translation of the study documentation by a locally approved interpreter/translator, it is the responsibility of the individual investigator to use locally approved translators.

28/06/2021 Version 1.2

Date and Version No:

Ethical committee review

Before the start of the study or implementation of any amendment we will obtain approval of the study protocol, protocol amendments, informed consent forms and other relevant documents (e.g. advertisements and GP information letters, if applicable) from the REC. All correspondence with the REC will be retained in the Study Master File/Investigator Site File.

Annual reports will be submitted to the REC in accordance with national requirements. It is the Chief Investigator's responsibility to produce the annual reports as required.

Study protocol amendments

Protocol amendments must be reviewed and agreement received from the Sponsor for all proposed amendments prior to submission to the REC.

The only circumstance in which an amendment may be initiated prior to REC approval is where the change is necessary to eliminate apparent, immediate risks to the patients (Urgent Safety Measures). In this case, accrual of new patients will be halted until the REC approval has been obtained.

Declaration of Helsinki and Good Clinical Practice

The study will be performed in accordance with the spirit and the letter of the declaration of Helsinki, the conditions and principles of Good Clinical Practice, the protocol and applicable local regulatory requirements and laws.

GCP training

All study staff must hold evidence of appropriate GCP training or undergo GCP training prior to undertaking any responsibilities on this study. This training should be updated every 2 years or in accordance with your Trust's policy.

7. ETHICS

7.1. Participant Confidentiality

The study staff will ensure that the participants' anonymity is maintained. Each participant will be allocated a unique study number and will be identified only by this number. The information linking each number and the details of each participant will be stored securely in a separate file. All data will be identified by the participant number only. All documents will be stored securely and only accessible by study staff and authorised personnel. The study will comply with the Data Protection Act which requires data to be anonymised as soon as it is practical to do so.

7.2. Other Ethical Considerations

Recruitment will be performed by a consultant neurosurgeon experienced in performing pineal region surgery. There will be no therapeutic promises, coercion or inducement of any sort.

A minimum of personal data and no participant-identifiable data will be gathered.

The only interventions are questionnaires and most questions are expansions of existing non-standardised symptom and lifestyle clinical interview caried in routine clinical practise.

8. DATA HANDLING AND RECORD KEEPING

All patient data will be anonymised. The participants will be identified by a study specific participant number. The information linking each number and the details of each participant will be stored securely in a separate file. All data will be identified by the participant number only. All data will be stored securely on Cambridge University Hospitals (CUH) NHS Trust computing clusters only. This is secure access and backed up automatically. No data will be stored on personal computers.

9. SPONSORSHIP, FINANCING AND INSURANCE

The study is jointly sponsored by the Cambridge University Hospitals NHS Foundation Trust.

All procedures will be done in NHS premises as part of the routine clinical care for patients.

Financing: No funding is required for this study as the amount of 'research-related' work is minimal and this work will be done on volunteer bases by the study participants and investigators.

10. POTENTIAL EXPANSIONS OF THE STUDY

This study may be expanded to a small number (one or two) of additional UK-based neurosurgical centres. Amendments to protocols and ethics application will be submitted as required prior to conducting any such potential expansions.

Nevins, E. J. et al. (2016) 'Incidental Pineal Cysts: Is Surveillance Necessary?', World neurosurgery, 90, pp. 96–102. doi: 10.1016/j.wneu.2016.02.092.

4. EORTC-QLQ-C30 Questionnaires

EORTC QLQ-C30 (version 3)

We are interested in some things about you and your health. Please answer all of the questions yourself by circling the number that best applies to you. There are no "right" or "wrong" answers. The information that you provide will remain strictly confidential.

Please fill in your initials:	
Your birthdate (Day, Month, Year):	
Today's date (Day, Month, Year):	31

		Not at	A Little	Quite a Bit	Very Much
1.	Do you have any trouble doing strenuous activities, like carrying a heavy shopping bag or a suitcase?	1	2	3	4
2.	Do you have any trouble taking a long walk?	1	2	3	4
3.	Do you have any trouble taking a short walk outside of the house?	1	2	3	4
4.	Do you need to stay in bed or a chair during the day?	1	2	3	4
5.	Do you need help with eating, dressing, washing yourself or using the toilet?	1	2	3	4

Du	ring the past week:	Not at All	A Little	Quite a Bit	Very Much
6.	Were you limited in doing either your work or other daily activities?	1	2	3	4
7.	Were you limited in pursuing your hobbies or other leisure time activities?	1	2	3	4
8.	Were you short of breath?	1	2	3	4
9.	Have you had pain?	1	2	3	4
10.	Did you need to rest?	1	2	3	4
11.	Have you had trouble sleeping?	1	2	3	4
12.	Have you felt weak?	1	2	3	4
13.	Have you lacked appetite?	1	2	3	4
14.	Have you felt nauseated?	1	2	3	4
15.	Have you vomited?	1	2	3	4
16.	Have you been constipated?	1	2	3	4

During the past we	eek:				1	Not at All	A Little	Quite a Bit	Very Much
17. Have you had diarrh	ea?					1	2	3	4
18. Were you tired?						1	2	3	4
19. Did pain interfere w	ith your daily a	activities?				1	2	3	4
20. Have you had difficultike reading a newsp						1	2	3	4
21. Did you feel tense?						1	2	3	4
22. Did you worry?						1	2	3	4
23. Did you feel irritable	e?					1	2	3	4
24. Did you feel depress	sed?					1	2	3	4
25. Have you had difficu	ulty rememberi	ng things?		\		1	2	3	4
	26. Has your physical condition or medical treatment interfered with your family life? 1 2 3 4							4	
27. Has your physical cointerfered with your			nt			1	2	3	4
28. Has your physical co- caused you financial		dical treatme	nt			1	2	3	4
For the following best applies to you 29. How would you rate					umber	bet	ween	1 and	7 that
2	3	4	5	6	7				
Very poor	Y				Excel	lent			
30. How would you rate	e your overall	quality of life	e during th	e past wee	ek?				
1 2	3	4	5	6	7				
Very poor					Excel	lent			

5. Study-specific questionnaire – preoperative

Pineal Cyst Questionnaire – BEFORE OPERATION

The information that you provide will remain strictly confidential.

Are yo	ou currently at work/school?	yes	no	
	If no, when did you last work?			
	What is your job?			
	Is it full time or part time job?	yes	no	
	If you are off work, is this because o	f the symរុ	otoms you came to	see me with?
		yes	no	

Weight

- now kg
- 1 year ago kg (approximately if not known precisely)
- 5 years ago or before symptoms started kg (approximately if not known precisely)

Do you think that there has been a relationship between weight and symptoms (presence of the symptoms or their severity)? yes no If yes, please, describe.

Medications

	Name	Started*	Stopped*
HRT			
Contraceptive pill			
Hormonal supplements			
Vitamins			
Painkillers			

^{*}Approximate date when you started and stopped taking this medication.

Have you had glandular fever	(= infectious mononucleosis)
------------------------------	------------------------------

yes no

Headache

Do you suffer from more than one type of headache (that are different in nature)? Please describe.

yes no

Do you suffer from migraines?

yes no

Do you have constant headache, i.e. headache that is there all the time and never really goes

away? yes no

If yes, when did it start?yearsmonths ago

Where in the head is your 'main headache'? (tick whichever apply to you)

Behind the eye – Left/Right

Behind the eyes

Between the eyes

On the back of the head

It is like a tight belt

On top of the head

In the centre of the head

Other (please describe)

Which word best describes your 'main headache'?

Sharp

Like a tight belt/band

Like a knife

Pulsating

Burning

Other (please describe)

When did the 'main headache' start?

Please give an approximate date

Please give an event, if there is one, that the headaches relate to

Did you 'main headache' start before my migraine headaches? yes no n/a

Does anything trigger your 'main headache'?

Sound/noise

Looking up

Light

Other (please describe)

What makes your 'main headache' worse?

Lying flat

Sitting up

Working on a computer

Any light

Fluorescent light

Noise

Other (list as many causes as you want)

When is your 'main headache' worst?

In the morning

In the evening

Any other time

There is no specific time of day when the headache tends to be worse than at other times

When is your 'main headache' least bad?

In the morning

In the evening

Any other time

There is no specific time of day when the headache tends to be better than at other times

Vision

Please tick all boxes next to the statements that apply to you

Blurred vision

Double vision

When turning my head I experience 'delay in seeing the object in front of me'

Tired eyes all the time

What makes your vision-related symptoms worse?

Light

Daylight

Fluorescing light

Computer light

Describe

Eye movement

Looking to the left

Looking to the right

Looking up

In any direction (is there any direction that makes things worse)

Time of day. My vision related problems are worse

Towards the end of the day

In the morning

At night

Do you have any problems when looking up? yes no

If yes – what happens/what symptoms you may get?

Balance problems - dizziness

Which of these statements best describes your symptoms?

I have a sensation of movement - as if I was on a rotating chair/the room is spinning

My legs feel week

I feel like have no control of my legs

I feel light-headed

Time profile

It is there all the time

It starts suddenly

It comes and goes. It lasts for

seconds minutes hours days

It is triggered by movement – describe what sort of movement(s)

Getting up

Suddenly moving my head sideways

Bending my head backwards

Stress

Loud noise

Closing eyes

Is anything that makes your balance worse?

Getting up

Suddenly moving my head sideways

Turning my head backwards

Stress

Loud noise

Closing eyes

Hearing

Reduced hearing problems on the

left right both sides

Hearing noises Hearing voices

Memory

Any memory problems? yes no

Please describe

Speaking

Any speech problems? yes no

Please describe

Concentration

Any problems yes no

Please describe

Sleep problems

I sleep too much

I sleep too little

Other sleep problems. Please describe

Other important symptoms

Please list and describe

Have you been seen by an ENT surgeon?	yes	no
What was their diagnosis/explanation?		
What treatment did they recommend?		
Have you been seen by an ophthalmologist?	yes	no
What was their diagnosis/explanation?		
What treatment did they recommend?		
Have you been seen by a neurologist?	yes	no
What was their diagnosis/explanation?		
What treatment did they recommend?		

6. Study-specific questionnaire – 3-month postoperative

Name sticker	į

Pineal Cyst Questionnaire – AFTER OPERATION at 3 months

The information that you provide will remain strictly confidential.

As compared to before the operation, overall, I am:

better worse no different

much better much worse

Are you currently at work/school? yes no

Your weight kg

Medications you currently take

	Name	Started	Stopped
HRT			
Contraceptive pill			
Hormonal supplements			
Vitamins			
Painkillers			

Headache

Please tick the box that best describes this symptom after the operation when compared to how it was before the operation.

better worse no different

much better much worse

I no longer have this symptom

I have never had this symptom

Vision

Please tick the box that best describes this symptom after the operation when compared to how it was before the operation.

better worse no different

much better much worse

I no longer have this symptom

I have never had this symptom

Hearing

Please tick the box that best describes this symptom after the operation when compared to how it was before the operation.

better worse no different

much better much worse

I no longer have this symptom

I have never had this symptom

Dizziness/balance problems

Please tick the box that best describes this symptom after the operation when compared to how it was before the operation.

better worse no different

much better much worse

I no longer have this symptom

I have never had this symptom

Memory

Please tick the box that best describes this symptom after the operation when compared to how it was before the operation.

better worse no different

I no longer have this symptom

I have never had this symptom

Speaking

Please tick the box that best describes this symptom after the operation when compared to how it was before the operation.

better worse no different

much better much worse

I no longer have this symptom

I have never had this symptom

Concentration

Please tick the box that best describes this symptom after the operation when compared to how it was before the operation.

better worse no different

much better much worse

I no longer have this symptom

I have never had this symptom

Sleep problems

Please tick the box that best describes this symptom after the operation when compared to how it was before the operation.

better worse no different

much better much worse

I no longer have this symptom

I have never had this symptom

Other symptoms that I had before the operation

Please tick the box that best describes this symptom after the operation when compared to how it was before the operation. Please name the symptom and use one of the descriptions from below:

Symptom 1:

better worse no different

much better much worse

I no longer have this symptom

Symptom 2:

better worse no different

Ino	longor	havo	+hic	cum	ntom
1110	longer	Have	uiis	Sylli	ρισπ

Symptom 3:

better much better	worse much worse	no different	
I no longer have thi			
i no longer nave tin	s symptom		
New symptoms that Please tick the box th how it was before the	at best describes th	-	ration when compared to
I have the following	g problems after the	e operation that I did not	have before the operation
Problem/symptom			score: 1-10*
		tom, i.e. score it based on a problem; "10" – it has r	n how much of a problem it made my life unbearable
I have no problems	that I can relate to	the operation	

7. Study-specific questionnaire -12-month postoperative

	1
	i
	1
	1
Name sticker	1

Pineal Cyst Questionnaire – AFTER OPERATION at 12 months

The information that you provide will remain strictly confidential.

As compared to before the operation, overall, I am:

better worse no different

much better much worse

Are you currently at work/school? yes no

Your weight kg

Medications you currently take

	Name	Started	Stopped
HRT			
Contraceptive pill			
Hormonal supplements			
Vitamins			
Painkillers			

Headache

Please tick the box that best describes this symptom after the operation when compared to how it was before the operation.

better worse no different

much better much worse

I no longer have this symptom

I have never had this symptom

Vision

Please tick the box that best describes this symptom after the operation when compared to how it was before the operation.

better worse no different

much better much worse

I no longer have this symptom

I have never had this symptom

Hearing

Please tick the box that best describes this symptom after the operation when compared to how it was before the operation.

better worse no different

much better much worse

I no longer have this symptom

I have never had this symptom

Dizziness/balance problems

Please tick the box that best describes this symptom after the operation when compared to how it was before the operation.

better worse no different

much better much worse

I no longer have this symptom

I have never had this symptom

Memory

Please tick the box that best describes this symptom after the operation when compared to how it was before the operation.

better worse no different

Speaking

Please tick the box that best describes this symptom after the operation when compared to how it was before the operation.

better worse no different

much better much worse

I no longer have this symptom

I have never had this symptom

Concentration

Please tick the box that best describes this symptom after the operation when compared to how it was before the operation.

better worse no different

much better much worse

I no longer have this symptom

I have never had this symptom

Sleep problems

Please tick the box that best describes this symptom after the operation when compared to how it was before the operation.

better worse no different

much better much worse

I no longer have this symptom

I have never had this symptom

Other symptoms that I had before the operation

Please tick the box that best describes this symptom after the operation when compared to how it was before the operation. Please name the symptom and use one of the descriptions from below:

Symptom 1:

better worse no different

much better much worse

I no longer have this symptom

Symptom 2:

better worse no different

I no longer have t	:his symptom		
Symptom 3:			
better	worse	no different	
much better	much worse		
I no longer have t	this symptom		
		e operation vis symptom after the opera	ation when compared to
I have the followi	ng problems after the	e operation that I did not h	ave before the operation
Problem/sympton	n		score: 1-10*
	•	tom, i.e. score it based on h a problem; "10" – it has m	
I have no probler	ns that I can relate to	the operation

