3.2.2. Symptoms – before and after surgery

We will determine the relative predictive values of individual symptoms and signs as well as their combinations in predicting improvement following resection of SPC. This will be done by comparing pre-operative and post-operative assessments at 3, 12, 24 and 36 months following resection of SPC.

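### On the pre-operative form, Balance, Hearing and Sleep have no answer for 'symptom absent', so a blank may mean absent or unanswered and these baseline predictors may be misclassified

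*Supplement*

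**What the plan says.** All references are to the protocol, Version 1.2, and its appended questionnaires.

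**Pre-operative form (appendix 5).** It has eight named symptom sections. Three have a symptom-level yes/no question: "Any memory problems? yes no", "Any speech problems? yes no" and, under Concentration, "Any problems yes no". The other five do not:

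- Headache has three narrower yes/no questions, on several headache types, on migraine and on constant headache ("Do you have constant headache, i.e. headache that is there all the time and never really goes" away).
- Vision has a list introduced by "Please tick all boxes next to the statements that apply to you" and one yes/no question about looking up.
- Balance begins with "Which of these statements best describes your symptoms", which presupposes the symptom.
- Hearing and Sleep are lists of complaints only.

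**Post-operative forms (appendices 6 and 7).** These do provide for absence. The 3-month form offers "I have never had this symptom" under all eight headings.

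**Use of the answers.** Section 3.2.2 states: "We will determine the relative predictive values of individual symptoms and signs as well as their combinations in predicting improvement". Section 3.3.2 and secondary outcome 6 in Section 4.4.2 put symptoms into a prediction model. Secondary outcome 4 compares baseline symptoms between the surgical and conservative cohorts.

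**Coding.** No rule for blanks is shown. Section 4.4.4 leaves detail to an analysis plan still to be written.

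**The concern.** Whether a symptom was present before surgery is the most basic predictor in these analyses. In Balance, Hearing and Sleep, a patient who does not have the symptom can only leave the section empty, and so can a patient who has it but skips that part of a long form.

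Neither simple coding works. Coding blanks as absent puts some patients with the symptom into the comparison group, which lowers the apparent prevalence and pulls the group difference towards zero. Coding blanks as missing removes the patients who truly lack the symptom, and so removes the comparison group. An analysis plan can choose between the two, but it cannot recover an answer that the form never asked for. Pre-operative status also cannot be asked afresh once the patient has been operated on.

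**Working it through.** **1. Count of sections.**

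| Section | Symptom-level 'no' on the form | Other sign that the section was worked through | Other baseline source |
|---|---|---|---|
| Memory, Speaking, Concentration | yes | not needed | not needed |
| Headache | no | three yes/no items | eligibility score, explicit 'No' |
| Vision | no | one yes/no item | eligibility score, explicit 'No' (visual disturbances) |
| Balance/dizziness | no | none | eligibility score, explicit 'No' (dizziness) |
| Sleep | no | none | QLQ-C30 item 11, scale from 'not at all' |
| Hearing | no | none | none |

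Five of eight sections lack a symptom-level negative answer. In three of those five (Balance, Hearing, Sleep) an empty section cannot be told from a skipped one on the form itself. In one (Hearing) nothing else at baseline settles it. The form does ask whether an ENT surgeon has been seen, but that does not record whether a hearing symptom is present.

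**2. Size if blanks are coded absent.** The documents give no completion rate and no prevalence for these sections, so both are assumed. Let *a* patients truly lack the symptom, and let *k* patients have it but skip the section. Let the mean outcomes be μ₁ (present) and μ₀ (absent), with skipping unrelated to outcome.

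- Mean in the recorded 'absent' group = (a·μ₀ + k·μ₁)/(a + k)
- Observed difference = (μ₁ − μ₀) × a/(a + k)
- Shrinkage = k/(a + k)

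With the planned N = 40 surgical patients:

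| Assumed prevalence | Present / absent | Skips k (share of those with the symptom) | Shrinkage |
|---|---|---|---|
| 30% | 12 / 28 | 2.4 (20%) | 2.4/30.4 = 8% |
| 50% | 20 / 20 | 2 (10%) | 2/22 = 9% |
| 80% | 32 / 8 | 3 (9%) | 3/11 = 27% |
| 80% | 32 / 8 | 4 (12.5%) | 4/12 = 33% |
| 80% | 32 / 8 | 6 (19%) | 6/14 = 43% |

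The effect is large only for common symptoms, where the 'absent' group is small and easily contaminated. With no skipping it is zero.

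**3. Primary endpoint.** The plan's own sample size reproduces. The SD of the difference is √(42² + 18² − 2 × 0.5 × 42 × 18) = √1332 = 36.5. A two-sided paired t-test at 5% for 20 points with 90% power then needs 37 participants. Role functioning comes from the QLQ-C30 and does not use this form, so nothing here changes it.

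**The case against.** The strongest reply is that most of the information exists elsewhere. Section 4.1 makes the symptom score part of eligibility, with an explicit 'No' for headache, dizziness and visual disturbances, and QLQ-C30 item 11 asks about trouble sleeping. This largely stands: it narrows the problem and supplies a better repair than later recall. It does not remove the problem. The score has no hearing or sleep item, and item 11 covers only the past week and not sleeping too much, which the form lists.

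A second reply is that coding of blanks belongs in the analysis plan. That is right, and the absence of a coding rule is not the complaint here. The gap is in the instrument.

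A third is that a changed form reaches only part of the cohort. Section 4 counts 21 patients operated on before the study began towards the 40, which leaves 40 − 21 = 19. This also stands, and is counted as a cost below.

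A reader might infer more than the documents support:

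- *That all five sections are equally ambiguous.* They are not. The yes/no items in Headache and Vision show whether the patient worked through the section, and the vision list asks for every statement that applies.
- *That the predictors are in fact misclassified, or that effects shrink by a third.* Neither is shown. Both need an unknown skip rate and an unstated coding rule, and the one-third figure also needs 80% prevalence.
- *That absence is recorded only after surgery.* This is wrong for headache, dizziness and visual disturbances, and largely wrong for trouble sleeping.

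Loss of layout in the published copy is an unlikely explanation, since printed yes/no answers survive elsewhere in the same form.

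**Conclusion.** The point holds in limited form and is minor. Balance, Hearing and Sleep lack a negative answer, so a blank there is ambiguous and these baseline predictors may be misclassified. Hearing is the one symptom with no other baseline source.

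The size cannot be fixed from the documents. Over the assumed non-zero skip rates shown it runs from about 8% or 9% shrinkage at 30% to 50% prevalence up to 27% to 43% at 80%. It is zero if nobody skips, or if blanks are resolved from other sources. These figures assume that blanks are coded absent and that skipping is unrelated to outcome.

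Only the secondary and exploratory predictor analyses and the baseline comparison of cohorts are touched. For conservative patients the point depends on whether they complete the same baseline form. The form shown is headed as a pre-operative one, and no separate conservative form is shown.

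**What to change.** **Patients still to be enrolled** (up to about 19 surgical patients, and conservative patients where the same baseline form is used): open Balance, Hearing and Sleep with a line such as 'Do you have this symptom? yes / no', as Memory, Speaking and Concentration already do. Add the same line to Headache and Vision for consistency.

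**Forms already completed**, including those of the 21 earlier surgical patients: state in the analysis plan that a blank section is resolved in this order.

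1. From baseline sources where recorded: the eligibility score for headache, dizziness and visual disturbances, and QLQ-C30 item 11 for trouble sleeping.
2. From a later "I have never had this symptom" answer, only as a fallback or in a sensitivity analysis, because it rests on recall after surgery and on the patient having returned a follow-up form.
3. Otherwise as missing.

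Report the number of blank sections per symptom, so that the size of the problem becomes visible.

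**Cost:** five printed lines and one coding rule. The baseline form would differ slightly between earlier and later patients, so form version would run broadly with the split before and after commencement and should be recorded. A few values would stay missing, mainly for hearing.
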